#### Statistical Analysis:

Feasibility outcomes will be reported for

- **Participant eligibility and recruitment:** This will be reported based on the people with RA screened, ineligible, eligible, consented and declined.
- Intervention adherence: Reported by the number of sessions completed out of 14.

- Usability and Acceptability: Scores from usability and acceptability questionnaires will be evaluated.
- Estimates of mean intervention effect and variance: Intervention effect sizes will be calculated from baseline to 7 sessions and baseline to 14 sessions for the patient-reported scores, HRV parameters of RMSSD and HF-HRV and blood inflammatory biomarkers.
- Adverse events/safety: Safety-related events and withdrawals will be reported in absolute numbers and as a percentage out of 12 participants.
- **Relationships between HRV biomarkers and pain measures:** A correlation between changes in HRV and changes in pain and pain sensitivity will be reported.

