#### **Objectives**

- 1. To determine if a future single-centre clinical trial of home-based taVNS is feasible in people with RA. This will be determined by
  - a. Estimating the proportion of patients with RA that meet the eligibility criteria.
  - b. Estimating how many eligible patients can be recruited.
  - c. Estimating the intervention adherence based on the percentage of the taVNS sessions started and completed.

- d. Evaluating the usability challenges and acceptability of in-home use of the prototype system and the user application.
- e. Identifying any adverse events/issues related to safety.
- 2. To explore potential dose-response relationships by estimating the mean intervention effect and variance on
  - a. Pain intensity (resting visual analogue scale (VAS), gripping VAS)
  - b. Pain sensitivity (pressure pain threshold)
  - c. Pain interference (Brief Pain Inventory)
  - d. Psychological distress (Depression, Anxiety and Stress Scale [DASS-21])
  - e. Health assessment (PGA [patient global assessment of disease activity] and HAQ [health assessment questionnaire])
  - f. C-reactive protein (CRP), Tumor Necrosis Factor-α (TNF-α), Interleukin (IL)-1β, IL-10 and IL-17A
  - g. Resting vagal tone (RMSSD, HF HRV), based on the assessment after the 7th and the 14th session.
- To determine whether HRV is a feasible biomarker for a future closed-loop taVNS device, we will explore the relationships between immediate post-taVNS change in HRV parameters and pain and pain sensitivity measures.

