#### **Study Design**

A single-arm, repeated measures feasibility study will be undertaken. Participants will receive 14 sessions of daily taVNS for 20 minutes. Two of these sessions will be supervised and take place at North Shore Hospital, as part of an assessment session, while 12 of these sessions will be completed unsupervised, in the participant's home. The participants will be required to visit North Shore Hospital for three 1-hour assessment sessions on day 1, day 8 and day 15, during which patient-reported outcomes, resting HRV, quantitative sensory testing and a blood sample of the participant will be collected for the evaluation of inflammatory biomarkers.

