#### **Participants**

Twelve participants will be recruited from the Rheumatology outpatient departments in the Auckland region. This sample size is based on the number of participants that have been considered feasible to

recruit over 6 months rather than any formal power calculation. Participants will be included based on the following criteria:

- Aged 18 years and over
- Diagnosed with adult-onset RA according to ACR/EULAR 2010 RA classification criteria
- Have the presence of at least 3/28 swollen and/or at least 3/28 tender joints with 1 tender joint being in the hand or wrists

Participants will be excluded from the study if they have any of the following:

- Ear infection (otitis media or otitis externa)
- Poor hand dexterity and no access to a helper at home who could assist in fitting the in-ear taVNS device and the respiration sensor strap
- Changes in oral or biologic disease-modifying antirheumatic drugs (DMARDs) in the last 4 weeks
- Have had intraarticular or intramuscular corticosteroids within 2 weeks prior to study entry
- Unstable dosing regimen of NSAIDs or analgesics in the last 2 weeks
- History of arrhythmia, myocardial infarction in the last 12 months, currently on beta-blocker medication or history of stroke affecting the brainstem
- Previous vagotomy
- Currently implanted electrical and/or neurostimulator device
- Active malignancy or history of active malignancy in the last 2 years, with the exception of nonmelanoma skin carcinoma or carcinoma in situ
- Severe comorbidities which in the judgement of the study physicians would deem the participant not suitable as it may impact the safety of study conduct
- Known cognitive impairments
- Psychiatric illness with active psychosis
- Pregnant

Participants will be free to withdraw from this study at any time without affecting their right to receive further treatment. In addition, participants may be withdrawn after the initial assessment session(s) if the study team determines that they do not have sufficient finger dexterity to fit and operate the equipment at home or a person living with them who is able to assist them. Finally, participants may be withdrawn if the study physicians ([name], [name]) consider it inappropriate for them to continue for any reason, including intervention-emergent adverse events, a serious adverse event, or medical reasons unrelated to the study. Reasons for withdrawal will always be documented and reported.

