**Estimates of mean intervention effect and variance**: Intervention effect sizes, using Cohen's d method [26], will be calculated from baseline to 7 sessions and baseline to 14 sessions for resting and grip pain intensity, pain interference, psychological distress, patient global assessment of disease activity, and health assessment questionnaire, SF36 pressure pain thresholds, resting vagal tone (RMSSD, HF-HRV) and inflammatory biomarkers (CRP, TNF- $\alpha$ , IL-1 $\beta$ , IL-10 and IL-17A).

**Relationships between HRV biomarkers and pain measures**: We will examine and report the relationships between changes in resting pain, grip pain, and pressure pain thresholds in each assessment

session (pre to immediately post 20 mins taVNS), and the change in each of the HRV parameters over the same time using Pearson correlation coefficients [27] or Spearman rank coefficients [28].

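### Objective 2 and the effect-size outcomes promise an intervention effect and a dose-response that a single arm on one common schedule cannot estimate

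*Protocol*

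**What the plan says.** Study Design, on allocation: "A single-arm, repeated measures feasibility study will be undertaken". On exposure: "Participants will receive 14 sessions of daily taVNS for 20 minutes". No control, sham or alternative dose level appears anywhere.

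Objective 2: "To explore potential dose-response relationships by estimating the mean intervention effect and variance on" pain, pain sensitivity, distress, health assessment, blood markers and resting vagal tone, assessed after the 7th and 14th session.

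Outcome measures says that intervention effect sizes, by Cohen's d, "will be calculated from baseline to 7 sessions and baseline to 14 sessions for resting and grip pain intensity" and for the other listed outcomes. The Synopsis (Statistical Analysis) lists the same quantity among the feasibility outcomes: "Estimates of mean intervention effect and variance: Intervention effect sizes will be calculated from baseline to 7 sessions and baseline to 14 sessions".

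On size, Participants says: "Twelve participants will be recruited from the Rheumatology outpatient departments in the Auckland region". The number rests on what is feasible to "recruit over 6 months rather than any formal power calculation".

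Two further places matter. Outcome measures reports adherence as one percentage out of 14, up to the final assessment. Study Procedures foresees missed sessions, with a message after one and a telephone call after two in a row.

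**The concern.** Two labels claim more than the design can give. An intervention effect is a contrast with what would have happened without the device, and nothing in this study supplies that comparison. A dose-response needs dose to vary separately from time, and here it does not.

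What is at stake is what the study may conclude. As written, the report could present an uncontrolled change as the effect of the device, and a difference between Day 8 and Day 15 as evidence that more sessions do more. Objective 2 cannot be met as worded, whatever the data show. This is fixed in the objective itself, so a statistical analysis plan could not repair it without rewording the objective.

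**Working it through.** **1. Planned dose against time.** Inputs: Study Design and Figure 2 of the Protocol, counting sessions up to the start of each visit.

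- Start of Day 8: 1 supervised (Day 1) + 6 at home (Days 2-7) = 7.
- Start of Day 15: 7 + 1 supervised (Day 8) + 6 at home (Days 9-14) = 14.

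This reproduces the Protocol's own 7 and 14. In general, planned sessions = visit day - 1, for every participant. Planned dose is an exact function of time, so no model fitted to these visits can attribute change to one rather than the other.

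**2. Actual dose.** Sessions received can differ only through missed sessions, which are not randomised and may be related to symptoms or tolerance. Someone who misses two of the six first-week home sessions arrives at Day 8 with 7 - 2 = 5 sessions, yet enters the contrast labelled 7 sessions. The adherence outcome is a single figure to the final assessment, so sessions received by Day 8 are not a planned output, although the application records starts and completions.

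**3. What the before-after change contains.** With one arm, observed mean change = device effect + change over time + placebo response + any regression to the mean. One equation cannot yield the first term. Entry requires at least 3 of 28 swollen and/or at least 3 of 28 tender joints, so some regression is possible. No threshold is set on any of the analysed outcomes, so its size cannot be derived from the Protocol.

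**4. Precision at n = 12.** The Protocol gives no expected d, so the values below are illustrative assumptions. They take d as mean change divided by the SD of change.

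For an observed d, t = d × √12 on 11 degrees of freedom. The 95% limits are the noncentrality values that put 2.5% in each tail, divided by √12. For d = 0.5, t = 0.5 × 3.464 = 1.73.

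| Observed d | 95% CI |
|---|---|
| 0.2 | -0.38 to 0.77 |
| 0.5 | -0.11 to 1.09 |
| 0.8 | 0.13 to 1.44 |

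The 95% interval for a mean change has half-width t(0.975, 11)/√12 = 0.64 SD of change. For an SD, the factors are √(11/χ²) at the upper and lower 2.5% points on 11 degrees of freedom: 0.71 to 1.70 times the estimate.

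These intervals express sampling error in the before-after change only. They say nothing about the mixture in step 3, which would remain with any number of participants.

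**5. SF36.** It stands in the Outcome measures list of effect sizes. It is not in Objective 2, is not named in Study Procedures (which gives questionnaires by example), and is not among the instruments in the Appendix.

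**The case against.** The strongest reply is that this is a wording matter on exploratory secondary outcomes. The dose-response aim is worded as exploring something potential. The before-after calculation is described openly. Stable usual care and a bar on medication changes during the 14 days limit one rival explanation. Actual exposure is already logged. As a descriptive summary of change in a feasibility study, the calculation is acceptable.

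Most of that stands, and it limits how serious the point is. It does not rescue the labels: exploratory wording does not make an unidentifiable quantity estimable, and stable medication does not remove placebo response, symptom fluctuation or the passage of time.

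A reader might go further and infer that these d values will size the future trial and make it too small. The Protocol does not support that. Objective 1 determines feasibility from eligibility, recruitment, adherence, usability and acceptability, and safety. No sentence commits d to a sample size calculation, and the present 12 does not rest on one. Any mis-sizing would depend on the later trial's analysis, which is not described.

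Nor can a figure be put on regression to the mean, because selection is on joint counts and those are not among the analysed outcomes. The choice of standardiser for d and the scale for skewed markers are commonly left to a statistical analysis plan, which is not shown, so they are no part of this point.

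**Conclusion.** The point holds as one of labelling and of what may be concluded. On the design as stated, planned dose and elapsed time coincide exactly, so Objective 2 cannot be met as a dose-response question, and the quantities called intervention effects are within-participant changes of mixed cause. Neither conclusion rests on a numerical assumption. The illustration of precision (d = 0.5, interval about -0.11 to 1.09) assumes all 12 participants contribute and d is taken on the SD of change; with fewer completers it would be wider. No stated figure in the Protocol is wrong, and the feasibility outcomes in Objective 1 are untouched. The change should be made, but it does not threaten the study.

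**What to change.** - In the Synopsis, Objective 2 and Outcome measures, rename the outcomes within-participant change from baseline to Day 8 and to Day 15, and replace dose-response with time course.
- Beside each change, report the number of sessions actually completed by that visit, from the application's records.
- Report mean change and SD of change with 95% confidence intervals.
- State that these changes will not be taken as a between-group intervention effect if a future trial is planned.
- Reconcile SF36: either remove it from the analysis list, or add it to the objectives, procedures and appended questionnaires.

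The cost is wording and a little reporting work. No new data are needed unless SF36 is kept and is not already collected. The real price is that the study can no longer claim an intervention effect size or a dose-response.

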#### Ethics, data management and responsibilities

#### **Ethics**

This study has received ethics approval from the Northern A Health and Disability Ethics Committee (reference **18139**). The study will be conducted according to the procedures specified in the study protocol, and in accordance with the principles of the "Declaration of Helsinki", CHMP GCP Guidelines on Good Clinical Practice E6(R2) and HDEC National Statement on Ethical Conduct in Research Involving Humans. All participants will be informed about the nature and objectives of the study and possible risks associated with participation. Written informed consent will be obtained from each participant before any study-specific activity is performed. The primary investigator will retain a copy of each participant's signed consent form. A copy of the signed and dated consent form will be provided to participants. Only participants who provide informed consent will enter the study.

#### Data management

Confidentiality will be maintained throughout the trial. Investigators involved in accessing health information are employees of the Te Whatu Ora and are bound by its relevant privacy and confidentiality policies. Co-investigators who are not Te Whatu Ora employees and any research assistants who become involved in data collection at a future date will be required to sign a confidentiality agreement. Upon signing a consent form, participants will be assigned a unique participant code and no personal identifiers (e.g. name, date of birth, contact details) will be contained in the main data set. Deidentified (coded) data (i.e. questionnaire responses, HRV data) will be collected on the Exsurgo application and will be sent to a central data storage point using end-to-end encryption. Coded data will be kept by Exsurgo in secure, HIPAA-compliant, cloud-based storage password-protected database. on а Any data transferred/downloaded from the database during the study (e.g. for data safety monitoring and/or data analysis purposes) will remain deidentified and stored on a password-protected computer or external hard drive. For qualitative interviews, participants will be asked to choose their pseudonym, which will not be associated with any other data apart from their unique participant code. All consent forms and data related to the trial will be securely stored for a period of at least ten years. Data backups will be completed on at least a weekly basis and all data will be checked using range checks for data values prior to data analysis.

#### **Roles and responsibilities**

Assoc. [name] is the primary investigator and will take overall responsibility for the conduct of the study, ensuring that it is conducted in accordance with both New Zealand law and Good Clinical Practice standards. [name] is responsible for notifying and seeking approval for any changes to the study protocol to HDEC and AUT and for ensuring that serious adverse events and intervention-emergent adverse events are reported to the sponsor, HDEC and Medsafe as required, as well as completing and submitting relevant progress reports.

[name] is the co-ordinating investigator and will be responsible for gaining written informed consent, organising participant appointments, data collection procedures and ensuring that data is managed and analysed in accordance with the data management plan. [name] will help to complete and submit relevant progress reports, under the supervision of Assoc [name].

Assoc Profs. [name] and [name] have contributed to the study design and will be involved in supervising data collection procedures and in the analysis and interpretation of data.

[name] [name] and Assoc. [name] have contributed to the study design and will act as the study physicians. They may be involved in recruitment as well as taking overall responsibility for medical supervision of the study. They will supervise the screening process and be involved in communications with the primary and co-ordinating investigators regarding the identification, coding and (if necessary) appropriate management of intervention-emergent adverse events. They will decide whether participants should be withdrawn from the trial for medical reasons.

All investigators will be involved in the dissemination of the study findings.

#### Role of the sponsor

The sponsor will have a role in supporting data collection and storage and access to the final reports before dissemination.

# Appendix

### **Brief Pain Inventory**

PLEASE USE BLACK INK PEN	Date: (mo Subject's In Study Sub ur lives, mos lave you had o n, shade in t	hth) (day) itials : ject #: Brief Pa t of us have ha pain other that he areas where	you feel pai	Sti Pri Re tory (SI time to tin ryday kind	udy Name: otocol #: wision: 07/0 hort Fc hort Fc ls of pain X on the Back	area that	headaches, sprains, and hurts the most.
3. Please rate y	our pain by i	marking the bo	x beside the	number ti	hat best d	lescribes	your pain at its worst
0 1 No Pain	2	3	4 🗌 5	6	7	8 []	9 10 Pain As Bad As You Can Imagine
4. Please rate least in the	your pain b last 24 hou	y marking the rs.	e box beside	e the num	ber that	best des	scribes your pain at its
0 1 No Pain	2	3	4 5	6	7	8 []	9 10 Pain As Bad As You Can Imagine
5. Please rate y	our pain by I	narking the bo	x beside the	number ti	hat best d	lescribes	your pain on the average.
0 1 No Pain	2	3	4 5	6	7	8	9 10 Pain As Bad As You Can Imagine
6. Please rate y	our pain by I	narking the bo	x beside the	number t	hat tells h	low much	pain you have right now.
☐ 0	2	3	4 🗌 5	6	7	8 🗌	9 10 Pain As Bad As You Can Imagine
Page 1 of 2		Co	pyright 1991 Cha Pain Res All right	arles S. Cleela earch Group s reserved	and, PhD		

1903 PLEASE USE BLACK INK PEN	Date: (mor Subject's In Study Subj	hth) (da itials :	(vi (vi	/ear) -	Study Na Protocol PI: Revision:	ame: #: 07/01/05			
7. What tre	atments or	medication	is are you	receiving	g for your	pain?			
				╡┤┝					
8. In the las mark the	st 24 hours box below	, how much the percent	relief hav	ve pain tre most sho	eatments ws how m	or medica nuch relie	ations pro of you ha	ovided? F	Please red.
0% 10% D No Relief	% 20% □	30%	40%	50%	60%	70%	80%	90%	100% Complete Relief
9. Mark the with you	e box beside r:	the number	that desc	ribes how	, during th	ne past 24	hours, pa	in has int	erfered
A. Gener 0 Does Not Interfere	al Activity	2 3	4	5	6	7	8 []	9	10 Completely Interferes
B. Mood 0 Does Not Interfere	]1 []:	2 ] 3	4	5 🗌	6	7	8 🗌	9	10 Completely Interferes
C. Walkin 0 Does Not Interfere	ng ability ]1 []:	2 3	4	5	6	7 []	8 []	9	Completely Interferes
D. Norma 0 Does Not Interfere	al Work (ir 1	ncludes b 2 3	oth work	coutside ⊡5	e the ho 6	me and 7	housew 8	ork) [] 9	Completely Interferes
E. Relation	onswitho	other peop 2 3	ole 4	5	6	7	8 🗌	9	10 Completely Interferes
F. Sleep 0 Does Not Interfere	]1 []:	2 3	4	5	6	7 []	8 []	9	Completely Interferes
G. Enjoy 0 Does Not Interfere	ment of lif	fe 2 □ 3	4	5	6	7	8 []	9	10 Completely Interferes
Page 2 of 2			Copyright 199 Pai A	)1 Charles S. n Research G Il rights reserv	Cleeland, Phi roup red	D			

Patien	t Assessn	nent		
Considering all the ways in which illness and healt make a mark below to show how you are doing:	h conditions	may affect yo	u at this time,	please
Very Well			Ve	ry Poorly
How much pain have you had because of your con- below to indicate how severe your pain has been:	dition over tl	he past week?	Place a mark	on the line
No Pain			Pai as I	n as Bad t Could Be
Please answer the following questions, even if you fee exactly as you think or feel – there are no right or wro	el that they m	ay not be relate Check the one	ed to you at this best answer for	s time. Answer each question.
Activity Level	Without any	With some	With much	Unable
Right now, are you able to:	difficulty	difficulty	difficulty	to do

 
Dress yourself, including tying shoelaces and doing buttons?
 
	0	1	2	3
2. Get in and out of bed?	0	1	2	3
3. Lift a full cup or glass to your mouth?	0	1	2	3
4. Walk outdoors on flat ground?	0	1	2	3
5. Wash and dry your entire body?	0	1	2	3
6. Bend down to pick up clothing from the floor?	0	1	2	3
7. Turn regular faucets on and off?	0	1	2	3
8. Get in and out of a car, bus, train or airplane?	0	1	2	3
9. Walk two miles?	0	1	2	3
10. Participate in sports and games as you like?	0	1	2	3
11. Out a constant data data 2	_			
12. De leit 6 d'année frankrige 1	0	1.1	2.2	3.3
12. Deal with feelings of anxiety or being nervous?	0	1.1	2.2	3.3
13. Deal with feelings of depression or feeling blue?	0	1.1	2.2	3.3
Your Name	Tod	ay's Date	Time	e of Day
Instructions for Office Sta	ff	]	Adapted from	
Activity Level Index Scoring: Visual Anal For FN (questions 1-10) add total with metric	og Scales: mo ruler. Line is	easure exactly	Pincus T, Swe Multidimensio Questionnaire 2230.	earingen C, Wolfe F. T onal Health Assessmer Arthritis Rheum 1999

### Health Assessment Questionnaire (HAQ)

Please try to answer each question, even if you do not think it is related to you at this time. There are no right or wrong answers. Please answer exactly as you think or feel. Thank-you.

#### 1. Please check (✓) the ONE best answer for your abilities OVER THE PAST WEEK:

OVER THE PAST WEEK Were you able to:	Without ANY Difficulty	With SOME Difficulty	With MUCH Difficulty	UNABLE To Do		
DRESSING & GROOMING a. Dress yourself, including tying shoelaces and doing buttons?						
b. Shampoo your hair?						

 
c. Stand up from an armless chair?
 
d. Get in and out of bed?
 
						

 
e. Cut your meat?
 
f. Lift a full cup or glass to your mouth?
 
g. Open a new milk carton?
 
WALKING
 
						

h. Walk outdoors on flat ground?

i. Climb up five steps?

						
Please check any AIDS OR DEVICES that you usually use for any of these activities:         Cane       Devices used for dressing (button hook, zipper puller, etc)         Walker       Built-up or special utensils         Crutches       Special or built up chair         Wheelchair       Other (specify):         Please check any categories for which you need HELP FROM ANOTHER PERSON         Dressing and Grooming       Eating						

 
HYGIENE
 
j. Wash and dry your entire body?
 
k. Take a tub bath?
 
l. Get on and off the toilet?
 
REACH
 
m. Reach and get a 5-lb object (such as a bag of n. sugar) from just above your head?
 
o. Bend down and pick up clothing from the floor?
 
GRIP
 
p. Open car doors?
 
q. Open jars which have been previously opened r. Turn faucets on and off?
 
ACTIVITIES
 
s. Run errands and shop?
 
t. Get in and out of a car?
 
	? ? ?					
u. Do chores such as vacuuming, yard work?			Please Tur	🗖 n Over 🏷		

	Raised toilet seat Bathtub seat Jar opener	
 
Long-handled appliance
 
Long-handled appliance
 
Bathtub bar
 
	s for reach s in bathroom	
Ple	ease check any categories f	or which you NEED HELP FROM	ANOTHER PERSON	i
	Hygience Reach	
 
Gripping and opening th
 
Errands and chores
 
	ings	
2.	How much PAIN have yo the scale below how severation of the scale below ho	u had because of your illness in ere your pain has been:	the PAST WEEK?	Please indicate
			]-[]-[]-[]-[] 7 8 9 10	VERY SEVERE PAIN
3.	How much of a problem WEEK?	has UNUSUAL fatigue or tiredne	ess been for you OV	ER THE PAST
	FATIGUE IS NO PROBLEM 0 1			FATIGUE IS A MAJOR PROBLEM
4.	How much of a problem	has sleeping been for you OVEF	R THE PAST WEEK?	{
	SLEEP IS NO PROBLEM 0 1			SLEEP IS A MAJOR PROBLEM
5.	How active has your arth	ritis been in the LAST 24 HOUR	S?	
	VERY WELL 0 1			VERY POORLY
6.	When you get up in the m If you answer NO pleas If you answer YES, ple until you are as limber	norning do you feel stiff? Se go to item number 7. As write the number of minutes: as you will be for the day?	ES 🗖 NO	er of hours:
7.	How do you feel today co	ompared to ONE MONTH AGO?	Please check only o	ne:
	MUCH BETTER(1)	BETTER(2) THE SAME(3)		NUCH WORSE
	14.0 DU ET	For office use only	1-0.125 7-0.875	13-1 625 10-2 3
			2=0.25 8=1.0 3=0.375 9=1.125 4=0.5 10=1.25 5=0.625 11=1.375 6=0.75 12=1.5	13-1.023         19-2.3           14=1.75         20=2.5           15=1.875         21=2.6           16=2.0         22=2.7           17=2.125         23=2.8           18=2.25         24=3.0
		0-0.5 Mild →0.5-1.0 Mild-M	od →1.0-1.5 Mod →1.5-2.0 M	Aod-Sev → 2.0-3.0 Se

